Aim 2: To determine if reductions in PM_{2.5} as a continuous variable are associated with significant reductions TNF α concentrations over a four-week period. For Aim 2, the design is identical to above; however in addition, we will collect PM_{2.5} data using commercially available PM sensors placed in the same bedroom as PAC. While it has been shown that PACs significantly lower indoor PM_{2.5} concentrations, these data will allow us to examine the effect of PM as a continuous variable in addition to the binary variable of PAC use (active versus sham). Commercially available PM monitors will record indoor PM_{2.5} concentrations using dual (backup) sensors, which store measurements on internal SD cards. Commercially available PM sensors have been well validated and use laser particle counters to count the number of particles at varying sizes with a sampling frequency of 2 minutes. PM monitors will be returned and data will be retrieved from SD cards at the post-intervention blood draw visit. These data will be measured for the entire cohort.

Exploratory Aim 1: To explore associations between PAC use and concentrations of cardiometabolic biomarkers using a targeted proteomic panel, the Olink Explore 384

Cardiometabolic panel, measured before and after 4 weeks of intervention. For this Aim, we will utilize additional data generated from the Olink panel. The Olink Explore Cardiometabolic panel is for research use only and will not be used toward FDA approval or diagnostic purposes. It will generate no clinically actionable results. The panel measures 369 protein biomarkers associated with cardiovascular and metabolic disease. This panel has been used to investigate cardiovascular disease treatment and prevention in various adult populations.^{18, 19} The pathways represented in the cardiometabolic panel include angiogenesis, cell activation, cell adhesion, coagulation, complement activation, extracellular matrix organization, response to hypoxia, and others. We will explore associations between PAC use (active vs. sham) and changes in circulating concentrations of Angiopoietin-1, ICAM-1, VCAM-1, PCSK9, sP-selectin, and BNP and other panel biomarkers. This Exploratory Aim will require no additional action on the part of participants.

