4.2 Study Endpoints

4.2.1 Primary Study Endpoints

Aim 1 and Aim 2: The primary study endpoint will be % change in concentration of TNF α over the 4-week intervention period calculated as:

$$\frac{([post - intervention] - [pre - intervention])}{[pre - intervention]} * 100\%$$

Because the baseline biomarker concentration for an individual is compared to post-intervention irrespective of range, percent change is a useful metric to compare reported results across assays.

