5.7 Participant Withdrawal or Termination

5.7.1 Reasons for Withdrawal or Termination

This is a minimal risk study, so we do not expect participants to withdraw for a safety related issue. However, participants are free to withdraw from participation in the study at any time upon request. If patients need to sleep elsewhere than their own bedroom for any unanticipated reason during the trial,

they should notify the research team and study endpoints (exposures and SBP) will be excluded from analyses during this period. Participants that unexpectedly require sleeping 2 or more consecutive nights away from their home (or a total of 7 days altogether) during the study period will need to drop from the study and their data will not be used in analyses. They can re-enroll at a later date.

Reasons for withdrawal may be moving from the area or simply not interested in participating further.

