6.1.4 Duration of Therapy

The PACs will be run continuously (24 hours per day) in participants' bedrooms for 4 weeks.

7 Study Procedures and Schedule

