7.6 Final Study Visit

Final Study Visit (Visit 2: 4 weeks after PAC turned on)

- Participants return study equipment: PM monitors, BP monitor data hubs, electricity monitors
- Collect blood for post-intervention biomarker measurement: <15 mL for all, additional ~10 mL for participants opting into future research.
- Final blood draw must occur ≤35 days from turning on PAC

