We will also utilize similar models incorporating PM_{2.5} as the independent variable in place of PAC arm. This will be assessed as the difference between pre-intervention baseline PM_{2.5} concentration and the time-weighted average concentration of PM_{2.5} from the 14-day intervention period. For our exploratory aim we will evaluate the Olink panel results using mixed-effects models for the remaining biomarkers that were not prespecified. Additionally, we will explore associations of PAC use with measured blood pressure in this clinical cohort that likely differs from our current pilot cohort recruited from a community setting. Because this pilot will integrate with our larger R01 trial, for which blood pressure is the primary outcome of interest, we will incorporate this biomarker data into that trial for a secondary exploratory analysis of biomarkers as mediators in the association between PAC use and blood pressure reductions.

In our exploratory analysis, there will be multiple testing bias due to utilizing a panel of 369 possible biomarker outcomes. With this size pilot cohort, it will be unlikely to achieve statistical significance if strict adjustments for multiple testing are undertaken. However, we will use the Holm procedure to evaluate for significance. Overall, these exploratory analyses will be hypothesis-generating and can help inform the design and sample size of future cohorts.

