Attachment B: Participant Instructions for Measuring Blood Pressure

Checking your blood pressure at home is an important part of this study and helps you know when your blood pressure is high. Here is a quick guide on how to check your blood pressure at home.

1. Please take two blood pressure readings 1 minute apart in the morning and two readings 1 minute apart in the evening for every day for 2 weeks (for a total of 4 per day, and 64 readings over the 2 weeks).
2. Make sure the air plug of the blood pressure cuff is placed tight into the machine before taking your blood pressure.
3. Remove tight-fitting clothing from the left upper arm.
4. Sit in a chair with your feet flat on the floor. Put your left arm on a table or armrest so the cuff is about the same height as your heart. Sit for at least 5 minutes prior to taking your first blood pressure reading.
5. Place the blood pressure cuff on the left upper arm so that the white stripe is on the inside of the arm. Place the bottom of the blood pressure cuff about 1/2 inch above the elbow. Make sure that the air tube is pointed downward – it should run down the inside of your forearm and be in line with your middle finger (with the palm up). **See next page for a diagram.**
6. Make sure that you are comfortable, and your left arm is not tense. Keep your left hand open.
7. Press the Start/Stop button once with your other hand to take a measurement. You should feel the blood pressure cuff tighten when the blood pressure is being taken. Do not move or talk, and stay relaxed. Wait until the cuff deflates and your blood pressure is showing on the display. Once that has occurred, remove the blood pressure cuff.

You can use this table to keep track of whether or not you have measured your blood pressure at these times (Example: place 2X's under Day 1 AM after you've collected your two morning readings)

Week 1 (date range: / / to / /)							
	Day 1	Day 2	Day 3	Day 4	Day 5	Day 6	Day 7
AM							
PM							
Week 2 (date range: / / to / /)							
	Day 8	Day 9	Day 10	Day 11	Day 12	Day 13	Day 14
AM							
PM							
Week 3 (date range: / / to / /)							
	Day 8	Day 9	Day 10	Day 11	Day 12	Day 13	Day 14
AM							
PM							
Week 4 (date range: / / to / /)							
	Day 8	Day 9	Day 10	Day 11	Day 12	Day 13	Day 14
AM							
PM							

[figure not shown]
[figure not shown]
HOW TO APPLY CUFF

1

Put your arm through the cuff loop.

2

Insert your arm as indicated by the marker.

[figure not shown]
3

Position the arm correctly.

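### The Aim 2 PM2.5 exposure is averaged over a 14-day intervention period, but the intervention and the TNFα change last 4 weeks and no 14-day exposure window is defined

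*Combined protocol and SAP*

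**What the plan says.** Only two places say how the Aim 2 exposure is calculated: the Statistical Analysis row of the Protocol Summary and section 10.3. Both use the same sentence. The exposure is the pre-intervention PM2.5 concentration minus a time-weighted average "from the 14-day intervention period".

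The rest of the protocol gives a different length for the intervention:

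- Section 6.1.4 has the air cleaners running continuously in participants' "bedrooms for 4 weeks".
- Section 4.2.1 sets the TNFα endpoint for Aims 1 and 2 as a percentage change "over the 4-week intervention period calculated as".
- Section 4.1 states Aim 2 itself over four weeks.
- Section 7.6 places the last visit 4 weeks after switch-on and adds: "Final blood draw must occur ≤35 days from turning on PAC".

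On data capture, section 4.1 says: "PM monitors will be returned and data will be retrieved from SD cards at the post-intervention blood draw visit". Section 5.7.1 deals with nights away from home: "study endpoints (exposures and SBP) will be excluded from analyses during this period".

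For blood pressure, section 4.1 (Exploratory Aim 2) asks for daily readings through the 4 weeks. Step 1 of Attachment B asks for readings "for every day for 2 weeks (for a total of 4 per day, and 64 readings over the 2 weeks".

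**The concern.** Aim 2 is one of the two specific aims, and PM2.5 reduction is its independent variable. As written, that variable is averaged over a period half as long as the scheduled interval over which the outcome changes. The wording describes the whole intervention period and gives it a length it does not have. It does not describe a chosen sub-window, so an analyst who followed it would have to decide after data collection whether to take the first 14 days, the last 14 days or some other set.

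The same PM2.5 change is used again. Section 4.2.2 defines the Exploratory Aim 2 endpoint as systolic pressure change as a function of PM2.5 change, and the Protocol Summary uses PM2.5 reduction as the exposure in the mediation analysis.

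The handout raises a lesser but related risk. PM2.5 can be averaged again from the stored record, but blood pressure readings that were never taken cannot be recovered.

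**Working it through.** **Inputs.** Averaging period: 14 days (Protocol Summary, section 10.3). Intervention: 4 weeks (sections 4.1, 4.2.1, 6.1.4, 7.6). Latest final draw: day 35 (section 7.6). Blood pressure: two readings each morning and evening, so 4 per day (section 4.1, Attachment B); printed total 64 (Attachment B).

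**1. Does 14 days match the intervention?** 4 × 7 = 28 days, so it does not.

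**2. Share of the exposure left out, read literally.**
- Nominal schedule: (28 − 14)/28 = 50%.
- Draw on day 35, with exposure counted to the draw: (35 − 14)/35 = 21/35 = 60%.
- Section 7.6 sets a latest day but no earliest. If a draw fell on day 26 (an assumed example), the share would be (26 − 14)/26 = 46%.
- Away-from-home periods removed under section 5.7.1 change the share further for each participant.

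So 50% is the nominal figure, not a minimum.

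**3. Does correcting 14 days to 4 weeks fully define the period?** Not quite. Stopping at day 28 or at the draw can differ by up to 35 − 28 = 7 days, which is 7/35 = 20% of the longest period. An end point has to be named.

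**4. How different could the two averages be?** The documents give no PM2.5 variances or correlations, so this part rests on assumptions. Let s be the between-home share of daily PM2.5 variance. With no day-to-day autocorrelation, the correlation between a 14-day mean and the 28-day mean that contains it is √{[s + (1 − s)/28] / [s + (1 − s)/14]}:
- s = 0: √(14/28) = 0.707
- s = 0.5: √(0.5179/0.5357) = 0.983
- s = 0.8: √(0.8071/0.8143) = 0.996

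With first-order daily autocorrelation of 0.5 or 0.8, taking the first or last 14 days, the correlations are 0.725 and 0.777 (s = 0), 0.961 and 0.937 (s = 0.5), and 0.989 and 0.980 (s = 0.8). The range is about 0.71 to 0.996. It concerns the on-treatment average only, not the difference from baseline and not the Aim 2 slope.

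**5. What is untouched?** The Aim 1 model and the power statement in section 10.4 use active versus sham as the exposure, so neither depends on this period.

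**6. Attachment B.** 4 × 14 = 56 and 4 × 28 = 112. The printed 64 corresponds to 64/4 = 16 days and fits neither. The log printed under the instructions has four weeks, but Weeks 3 and 4 repeat the labels Day 8 to Day 14. A participant who stopped at day 14 would have 2 × 14 = 28 scheduled morning readings instead of 2 × 28 = 56, before the up to 30% missing readings that section 4.1 anticipates.

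**The case against.** The strongest reply is that this is a wrong number with little consequence. Every design section says 4 weeks. The PM2.5 record stays on the monitors until the final visit, and section 10.5.1 has it processed afterwards by staff blinded to arm. If the number is corrected before analysis, nothing is lost. That stands, and it limits the point to a correction of the text. It does not remove the point, because the two affected sentences are the only definition of the exposure and they disagree with the rest of the protocol.

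It is also fair to say that a visit window around week 4 is ordinary, and that Attachment B is a handout which section 19 places outside the protocol. Both items are therefore secondary. The handout's four-week log, the verbal instructions, the optional reminders and the real-time dashboard make an early stop possible rather than likely.

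A reader might infer more than the documents support:

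- That no 14-day period appears anywhere in the trial. Attachment B does ask for 2 weeks of readings, but for blood pressure only. What is absent is a 14-day intervention or PM2.5 window.
- That at least half of the exposure days must be lost. Step 2 shows why 50% is not a lower bound.
- That the Aim 2 slope is biased or materially weakened. Nothing in the documents allows that to be calculated, and the assumed range in step 4 runs from a sizeable loss to almost none.
- That an early stop in blood pressure readings would touch Exploratory Aim 2 alone. The second exclusion criterion in section 5.2 also uses average home readings over any 10-day period.
- That the 14 days were carried over from earlier work. The background cites a meta-analysis with a median of 13.5 days, but the protocol does not link the two.

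**Conclusion.** The definition of the Aim 2 exposure is wrong as written and should be corrected before analysis. It gives the intervention period as 14 days where the protocol otherwise sets 4 weeks, and it does not identify which 14 days. Read literally, half of the recorded PM2.5 days on the nominal schedule (14 of 28) fall outside the exposure. That figure assumes a day-28 draw and no away-from-home exclusions. No effect on the Aim 2 slope is claimed. Exploratory Aim 2 shares the affected variable. The inconsistency between Attachment B and section 4.1 is a separate, minor defect that should be reconciled at the same time.

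**What to change.** In the Protocol Summary and section 10.3, replace the 14-day figure with the 4-week intervention period. Run it from switch-on of the air cleaner to a stated end point, either day 28 or the final blood draw, subject to the exclusions in section 5.7.1. If a 14-day sub-window was really intended, the text must say which days and why.

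Reconcile Attachment B's recording period, reading total and Week 3 and Week 4 day labels with section 4.1.

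This edit settles the on-treatment average only. How the pre-intervention PM2.5 level is measured is a separate question that it leaves open: section 7.5 and Attachment C set up the monitor and the air cleaner together.

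The cost is one number in two places, one sentence on the end point and a corrected handout. Under section 13.2 the amendment needs IRB approval before it is implemented, and participant materials are also submitted to the IRB. Section 19 means that the attachment needs no protocol amendment. No data collection is added beyond what section 4.1 already plans.

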Brief Summary	
In this research, we will conduct a double-blind, sham-controlled, randomized trial to examine the impact on cardiometabolic biomarkers of air pollution exposure reduction using home portable air cleaners (PACs) in a cohort of current adult patients at NYU Langone Health. This study is funded by CTSI (NIH/NCATS UL1TR001445) with two primary aims and two secondary/exploratory aims. In Aim 1, we will evaluate associations with PAC use with a priori specified biomarker of inflammation, tumor necrosis factor alpha (TNFα). We will determine if 4 weeks of home air filtration with PACs compared to sham is associated with significant reductions in TNFα concentrations when measured before and after intervention. Blood samples will be collected from 44 study participants before and after 4 weeks of PAC use (true and sham) for biomarker concentration measurement. In Aim 2, we will determine if reductions in fine particulate matter (<2.5 μm in diameter, PM_{2.5}) as a continuous variable are associated with significant reductions TNFα concentrations over a four-week period. In Exploratory Aim 1, we will explore associations between PAC use and concentrations of cardiometabolic biomarkers using a targeted proteomic panel, the Olink Explore 384 Cardiometabolic panel, measured before and after 4 weeks of intervention. This will be a hypothesis-generating analysis to identify possible novel biomarkers and pathways that may have importance in the physiological responses and clinical outcomes associated with air pollution exposure. In Exploratory Aim 2, we will explore if biomarkers identified in Exploratory Aim 1 with significant reductions after 4 weeks of PAC partially mediate the association between reductions in PM_{2.5} and changes in daily home blood pressure (BP) measurements. Participants will be given home BP monitors to transmit de-identified daily morning BP measurements to a secure database during the 4 week intervention period. Changes in morning systolic (BP) will be analyzed as the outcome of interest, with changes in biomarker concentrations evaluated as a mediator of the relations between pollution reduction and changes in BP.

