Statistical Analysis	
For all Aims: descriptive summary statistics, such as mean and standard deviation (or median and inter quartile range) will be reported for continuous variables and counts and proportions for categorical variables. Graphical displays of all variables will be examined, with attention to assessing balance in these characteristics by intervention group, and with assessment of the distribution of variables, relevant to the choice of statistical tests. Statistical comparisons between the PAC and sham groups will be performed using a two-group two-sided t-test or nonparametric Wilcoxon test for continuous variables and Chi-square test for categorical variables. Distributions of biomarker concentrations will be examined and non-normally distributed concentrations will be log-transformed, as needed.
 
The analysis of our primary outcome for Aim 1 will use linear mixed-effects models with the change in prespecified biomarker, from pre-intervention to post-intervention, concentrations as the dependent variable and treatment arm as the independent variable. While randomization should obviate the need for additional adjustment, models will be adjusted for age, gender and BMI, as these are known to be related to inflammatory biomarker concentrations. These models use subject-specific random intercepts to account for heterogeneity between subjects and will account for within subject correlation between biomarker observations.
 
For Aim 2, we will also utilize similar models incorporating $PM_{2.5}$ as the independent variable. This will be assessed as the difference between pre-intervention baseline $PM_{2.5}$ concentration and the time-weighted average concentration of $PM_{2.5}$ from the 14-day intervention period.
 
For Exploratory Aim 1, we will evaluate the Olink panel results using mixed-effects models for the remaining biomarkers that were not prespecified. These will be the same models as for Aims 1 and 2, adjusted for age, gender, and BMI. For Exploratory Aim 2, we will evaluate associations of PAC use and $PM_{2.5}$ reduction with measured AM systolic blood pressure in this clinical cohort. We will perform mediation analysis using biomarkers with significant associations in Exploratory Aim 1 as mediators of the relations between $PM_{2.5}$ reduction and change in blood pressure.

Schematic of Study Design

1 Key Roles

Principal Investigator

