3.1 Primary Objective

The primary objective of this research is to examine the effectiveness of PAC use in improving inflammation related to cardiovascular disease.

Specific Aim 1: To determine if 4 weeks of home air filtration with PACs compared to sham is associated with significant reductions in TNF α concentrations when measured before and after intervention.

Specific Aim 2: To determine if reductions in PM $_{2.5}$ as a continuous variable are associated with significant reductions TNF α concentrations over a four-week period.

Exploratory Aim 1: To explore associations between PAC use and concentrations of cardiometabolic biomarkers using a targeted proteomic panel, the Olink Explore 384 Cardiometabolic panel, measured before and after 4 weeks of intervention.

Exploratory Aim 2: To explore if changes in TNF α and other novel cardiometabolic biomarkers partially mediate the effects of PACs on home blood pressure.

4 Study Design and Endpoints

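### Holm over 369 proteins appears to gate the panel mediation step, which at 44 enrolled is likely to have no panel protein to test, and no fallback is given.

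*Combined protocol and SAP*

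**What the plan says.** Section 10.3 acknowledges that "there will be multiple testing bias due to utilizing a panel of 369 possible biomarker outcomes" and that, in a pilot of this size, "it will be unlikely to achieve statistical significance if strict adjustments for multiple testing are undertaken". It then sets the rule: "However, we will use the Holm procedure to evaluate for significance". No other significance rule is given for the panel. The section calls these analyses hypothesis-generating.

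Entry to the mediation analysis is described in several places:

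- **Protocol Summary, Statistical Analysis:** "We will perform mediation analysis using biomarkers with significant associations in Exploratory Aim 1 as mediators".
- **Protocol Summary, Brief Summary:** "we will explore if biomarkers identified in Exploratory Aim 1 with significant reductions after 4 weeks of PAC", with mediation of the PM2.5 to blood pressure association as the question.
- **Protocol Summary, Objectives:** the mediators are the novel biomarkers that Exploratory Aim 1 identifies.
- **Sections 3.1 and 4.1, Exploratory Aim 2:** the question is whether TNFα and "other novel cardiometabolic biomarkers partially mediate the effects of PACs on home blood pressure". Section 4.1 then speaks of significant biomarkers without giving a threshold.

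Section 4.1 lists the proteins for Exploratory Aim 1 as "Angiopoietin-1, ICAM-1, VCAM-1, PCSK9, sP-selectin, and BNP and other panel biomarkers"; section 2.1 names the same six. No separate analysis is planned for them. The plan does not say what happens to the mediation step if no protein qualifies.

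**The concern.** A family-wise procedure over 369 tests is built to avoid even one false positive. Here it is the only rule available for deciding which proteins go forward from a screen whose purpose is to find leads. If almost nothing can pass, the panel-protein part of Exploratory Aim 2 has no input. Choosing mediators after seeing an empty list would be a data-driven choice.

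The candidate set is also inconsistent. Sections 3.1 and 4.1 include TNFα. The Summary draws mediators from Exploratory Aim 1, which in its analysis text covers the biomarkers that were not prespecified. TNFα is the prespecified one, so it drops out under that wording.

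**Working it through.** **Inputs**

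- Panel size m = 369 (4.1, 10.3).
- Alpha 0.05, above 80% power at 66, and up to 10% dropout (10.4). Two-sided testing is assumed.
- Enrolment 44 (Protocol Summary, 5.4, 10.4), giving 44 × 0.9 = 39.6, about 40 completers.
- The alternative figure of 74 (4.1, 5.6), giving 74 × 0.9 = 66.6, about 66 completers.
- SD and standardised effect: not stated.

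**1. The plan's own figure.** The 66 cannot be reproduced without an SD. The dropout step can: 66 / 0.9 = 73.3, rounded up to 74, so 66 is consistent with a completer count.

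**2. Implied effect.** Use a noncentral t for two equal arms with three covariates, df = n − 5 and noncentrality d√(n/4). Solving for exactly 80% power at n = 66 gives d = 0.70. For the planned 10% change this implies an SD of about 14.3%. If 66 already included dropout (about 60 analysed), d = 0.74.

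**3. Power per protein.** Holm's first threshold is 0.05/369 = 0.000136.

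| Completers | Alpha | Power at d = 0.70 |
|---|---|---|
| 40 | 0.05 | 58% |
| 40 | 0.05/369 | 3.4% |
| 66 | 0.05/369 | 12.8% |

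With 40 completers the range at 0.05/369 is 3.4% to 6.3%, depending on t or normal formula and on d solved at 66 or 60. A single protein would need d of about 1.64 for 80% power.

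**4. Chance that any panel protein passes.** Holm's first step is Bonferroni. With k truly shifted independent proteins, P(any) = 1 − (1 − power)^k × (1 − 0.05/369)^(369−k).

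For 40 completers and k = 10: 1 − (1 − 0.0343)^10 × (1 − 0.0001355)^359 = 0.328.

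| k truly shifted | 40, independent | 40, correlation 0.3 | 40, correlation 0.5 | 66, independent |
|---|---|---|---|---|
| 1 | 8% | 7% | 6% | 17% |
| 5 | 20% | 17% | 15% | 52% |
| 10 | 33% | 27% | 22% | about 75% |
| 20 | 53% | 40% | 32% | 94% |

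The correlated columns come from a simulation with one common factor. With 40 completers the chance first exceeds one half at about 19 independent proteins (about 12 by the normal formula); with 66 completers, at about 5.

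**5. What other rules would do** (40 completers, 10 shifted proteins). Under independence, Benjamini-Hochberg lists at least one protein in about 50% of trials at 10% FDR and about 69% at 20%, with on average about 0.2 and 0.7 false leads. With correlation of 0.3 to 0.5, mean false leads rise to about 1.2 to 3.3 at 10% and 4.1 to 8.9 at 20%. Holm over only the six named proteins (first step 0.05/6 = 0.0083) gives about 30% power per protein.

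**The case against.** Several points on the other side stand.

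- **The gate is inferred.** No sentence says that mediators are chosen on Holm-adjusted results. However, Holm is the only rule stated for the panel. If another threshold was meant, it is not in the plan.
- **A reader might infer that Exploratory Aim 2 could not be carried out at all.** The documents do not support that. Sections 3.1 and 4.1 name TNFα as a mediator, and it is tested in Aim 1, outside the panel screen. The endpoint in 4.2.2 relates change in morning systolic pressure to change in PM2.5, and the Summary also relates PAC use to that pressure. Neither analysis needs a mediator. Section 10.3 also carries the biomarker data into a larger trial for a mediator analysis, although that does not supply a rule for this pilot.
- **A reader might infer that an empty list is certain.** The plan says only that significance is unlikely. The probability depends on an unstated SD, on how many proteins respond, and on enrolment; at 74 enrolled with 10 independent responders, a pass is the likelier result.
- **The limitation is disclosed and the aim is exploratory.** The primary analysis is untouched. Section 4.1 lists the six proteins alongside the rest of the panel and promises them no priority.
- **FDR screening has a cost.** False leads rise sharply under correlation, and at 10% FDR the list is still empty in about half of trials or more.

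These points narrow the concern to the panel-protein mediation step. They do not supply a fallback or reconcile the two accounts of which biomarkers are candidates.

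**Conclusion.** The concern holds for the panel-protein mediation step. At 44 enrolled, with Holm read as the gate, that step is more likely than not to be empty unless about 19 or more independent proteins, or more if they are correlated, shift by the full planning effect. With 10 responders the chance that any protein passes is about 33% if independent and 22% to 27% if correlated at 0.3 to 0.5. These figures assume two-sided tests, d back-solved from exactly 80% power at 66, and the same effect in every responding protein. The conclusion turns on 44 being the operative enrolment figure, as 10.4 indicates by tying it to budget. Separately, and whatever the power, the Summary and sections 3.1 and 4.1 disagree on whether TNFα is a candidate mediator. The right grade is a cheap improvement to an exploratory aim.

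**What to change.** 1. **Main repair.** Name TNFα and the six proteins listed in 2.1 and 4.1 as candidate mediators, analysed whether or not they reach significance. Use the same rule in the Protocol Summary (Brief Summary, Objectives, Statistical Analysis), 3.1, 4.1 and 10.3.
2. **Rest of the panel.** Screen with Benjamini-Hochberg at one FDR fixed in advance (for example 10% or 20%), report q-values, and label any mediator selected this way exploratory. Keep Holm for any claim of statistical significance.
3. **Enrolment.** Reconcile 44 with 74, since the expected yield of the screen depends on it.

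The cost is wording only, with no added participants, visits or assays. The downside is the extra false leads: on average below one if proteins are independent, and about 1 to 9 if correlated at 0.3 to 0.5, depending on the FDR chosen. Because the FDR screen can itself come back empty, it does not replace item 1.
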